4.2.1.3. Run-In Period (Part A)

For two weeks prior to Day 1 of the DFU Treatment Period, subjects will receive standard-of-care. For all diabetic subjects in Part A, each subject's DFU will be measured at screening and Day 1; if, after 14 (± 1 day) days from screening, the subject's DFU has reduced in size by greater than 30 %, the subject will not be randomized to receive investigational product. If Screening and Day 1 are not 14 days (± 1 day) apart, an additional visit (Optional Baseline Run-In) will need to be scheduled prior to Day 1 to meet the Run-In requirement. Subjects that do not meet randomization eligibility will be discontinued from the study.

4.2.1.4. Cohort 2 (Part A)

Cohort 2 will enroll DFU subjects who fulfill screening criteria. Subjects will be randomized to receive a single application of GSK1278863 or placebo in two dosing periods. The two dosing periods are intended to provide a 'within patient' comparison of PK between application to intact skin and to DFU. The first application will be made on intact skin, followed by a 10-day washout period. Blood for serial PK sampling will be collected out to 72 hours post-dose. After review of safety, tolerability and PK data, these subjects will then receive an application of the same dose directly to the DFU.

Subjects will come in to the clinic fasting early in the morning of Day 1 of each dosing period and will follow the same schedule as Cohort 1, with the exception that the first application will be on intact skin, and the application in the second dosing period will be directly to the DFU. See Section [4.6.1](#) for detailed timing of assessments and sampling.

4.2.1.5. Cohorts 3 and 4 (Part A)

Cohorts 3 and 4 will enroll DFU subjects who fulfill screening criteria. Subjects will be randomized to receive either GSK1278863 or placebo. Each cohort will evaluate a new dose of GSK1278863, with applications made directly to the DFU. If subjects are re-enrolling from a previous cohort, they must complete the second Follow-up visit (Day 28-32 post last dose) and therefore the 14 day Run-in period may begin 14 days prior to this visit. If Cohort 4 is the final cohort, subjects will also receive application to intact skin.

Subjects in Cohort 3 will come in to the clinic fasting early in the morning of Day 1 and will follow the assessments as outlined in Section [4.6.1](#).

Cohort 4, or the final cohort if optional cohorts are enrolled, will have 2 dosing periods (10 day washout between periods), with GSK1278863 applied directly to the DFU in dosing period one and followed by application to intact skin in the second dosing period. Subjects will follow the same schedule as for Cohorts 1 and 2. See Section [4.6.1](#) for detailed timing of assessments and sampling.

4.2.1.6. Optional Cohorts (Part A)

Additional cohorts may be added as necessary to obtain relevant data for determination of starting doses for the repeat (Part B) portion of the study.

- If the data from Cohort 4 are considered sufficient to establish dosing for Part B, subjects from that cohort will be asked to return to the clinic for a SD administration of the compound to intact skin in order to make comparisons of systemic PK for linearity between low and high doses and a within-patient comparison of application of drug to intact skin versus DFU.
- If however, the data are NOT sufficient to establish dosing for the repeat dose section of the protocol, another cohort will be recruited for application of an additional dose to their DFU. This process will be repeated until sufficient data are collected to establish dosing for Part B. Once this is established, the last cohort will be asked to return for application of the compound to intact skin for the comparisons as described above.

Subjects of the cohort asked to return for application of the compound to intact skin will undergo PK sampling at time points established by the findings of the kinetics in the previous cohorts.

The timing of the final cohort, in which application to intact skin is assessed, may overlap with the first cohort of Part B, as long as all doses of GSK1278863 in previous cohorts are well tolerated and provide sufficient PK for Part B predictions. Systemic exposures may or may not permit predictions for dose selection and therefore dose determination will be selected based on available safety and tolerability data.

GSK1278863 PK data from the cohorts of Part A will be used for the predictions of the expected systemic exposures in Part B (data permitting). Preliminary safety, tolerability and PK data will be reviewed before initiating the randomized repeat-dosing period of Part B at approximately the same time as the final cohort in Part A.

4.2.1.7. Follow-up Visits

Follow-up visits will occur 7 to 10 days and 28 to 32 days following completion of dosing. Any subject withdrawing from the trial prematurely will also be asked to complete all follow-up procedures.

See Section 4.6 for details regarding all study procedures performed during the course of this trial.

4.2.2. Part B –Repeat Doses in Diabetic Foot Ulcer Subjects (Cohorts 5, 6 and 7)

Part B will include approximately 3 cohorts. Enough subjects will be enrolled in each cohort to complete approximately 16 diabetic subjects with diabetic foot ulcer. All subjects will receive standard of care (SoC; Section 7.4) up to randomization, and then will be randomized to one of three arms, a) 12 active drug + SoC, b) 2 SoC, and c) 2 placebo + SoC). The randomized repeat application in Part B may start after dosing in Cohort 4 of GSK1278863 has been found to be safe and well tolerated.

Doses for the cohorts in Part B will be determined from safety, tolerability and PK data from Part A. Each cohort will enroll a new group of subjects, randomized to either the

same dose, ascending dose or descending dose of GSK1278863. All applications in Part B will be made directly to the subject's DFU.

For each cohort, subjects will undergo repeat applications of GSK1278863 or placebo, at the dose chosen for that cohort for 14 days. The first day of the 14-day repeat application period will be conducted in the clinic. Subjects will return to the clinic as indicated in Section 4.6.2, and applications between visits will be performed by the subject at home.

Blood for PK sampling will be collected on Days 1, 7, 14 and 15. See Section 4.6.3 for specific time points for drawing samples.

There will be approximately one week between cohorts to allow for review of preliminary safety, tolerability and PK data before proceeding to the next cohort. Pharmacodynamic data, where available, may be obtained for review.

Subjects may not participate in more than one cohort in Part B. Subjects may participate in Part A and then Part B which will require the subject to be screened again.

4.2.2.1. Screening (Part B)

To determine subject eligibility for enrollment in the study, a screening visit will be performed within approximately 28 days of first dose administration. For the purposes of subject eligibility for enrollment in the study, screening assessments are defined as any assessments performed prior to the first dose of study drug in each part.

If a subject is not eligible for the study based on the Inclusion and Exclusion Criteria at the initial attempt, but becomes eligible at a later date during the enrollment period, the investigator should contact the GSK Medical Monitor to discuss the possibility of re-screening the subject.

4.2.2.2. Run-In Period (Part B)

For two weeks prior to Day 1 of the Treatment Period, subjects will receive standard-of-care as described in Section 7.4. For all subjects in Part B, each subject's DFU will be measured at screening and Day 1; if, after 14 days from screening, the subject's DFU has reduced in size by greater than 30 %, the subject will not be randomized to receive investigational product and is considered a Run In Failure. If Screening and Day 1 are not 14 days (± 1 day) apart, an additional visit (Optional Baseline Run In) will need to be scheduled prior to Day 1 to meet the Run In requirement. Subjects that do not meet randomization eligibility will be discontinued from the study.

4.2.2.3. Treatment Period – (Part B)

Cohorts 5, 6 and 7 (numbering assumes no optional cohorts are enrolled in Part A) will each enroll sufficient subjects so that approximately 48 DFU patients who fulfill screening criteria complete all study visits. Doses selected for these cohorts will be chosen based on preliminary safety data and PK results from Part A of this study.

14-Day Dosing (Part B)

Subjects will be randomized to receive applications of GSK1278863 or placebo directly to the DFU on Day 1 for evaluation of safety and tolerability, PK of GSK1278863 and PD. Applications of study drug will be done in clinic on Days 1, 4, 7, and 14. Subjects are responsible for study drug application on Days 2-3, 5- 6 and 8-13.

It should be noted that on days where serial PK sampling occurs it is permissible to allow subjects to check out of the clinic after the 8 hour PK time point has been collected as long as the subject can return for sample collection within the 10 to 12 hour PK window. If subjects elect to stay overnight, they should be encouraged to apply the study ointment and complete the diary entries themselves before being discharged in the morning. Study staff can take this opportunity to provide additional instruction to subjects.

Subjects will be given detailed instructions for application of GSK1278863 at home, and enough study drug for applications at home between clinic visits. See Section [11.1](#) for further instructions on at-home dosing.

Doses for subsequent cohorts may be adjusted based on PK results, and/or safety and tolerability data.

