4.2.2.4. Follow-up Visits

Follow-up visits will occur 7 to 10 days and 28 to 32 days following completion of dosing. Any subject withdrawing from the trial prematurely will also be asked to complete all follow-up procedures.

See Section [4.6](#) for details regarding all study procedures performed during the course of this trial.

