4.6.2. Time and Events Table Part B

Procedures	Screening	Optional Baseline Run In Visit ¹	Day 1	Day 4	Day 7	Day 14	Day 15	Follow-up	
Visit Window (relative to Day 1)	-28 to -14 days		Exams/samples pre-dose					7-10 days post last dose	
Clinic Visit	X	X	X	X	X	X	X	X	X
Informed Consent	X								
Demographics	X								
Complete physical	X								
Brief physical		X	X	X	X	X	X	X	X
Medical/medication/drug/alcohol history	X	X							
12-lead ECG ²	X		X				X		
Vital signs ³	X		X		X		X	X	X
Urine pregnancy(females)	X		X					X	
Hema/Chem/ Safety Labs ⁴	X		X		X		X	X	
Vascular Perfusion Eligibility Assessments ⁵	X								
Blood samples for HIF α , (e.g., EPO, Hepcidin, VEGF) ⁶			X		X		X		
Standard of Care Treatment ⁷	X	X	<=====>					X	X
Study Treatment/Dosing In the Clinic ⁸			X	X	X	X			

Procedures	Screening	Optional Baseline Run In Visit ¹	Day 1	Day 4	Day 7	Day 14	Day 15	Follow-up	
PK serial blood sampling ⁹			X		X	X	X		
PK Trough Sample ⁹									
Tissue Biopsies (gene expression, macrophage and bioburden analysis) ¹⁰			X		X		X		
Wound Fluid (cytokine and bioburden analysis) ¹¹			X		X		X	X	
SensiLase (Doppler blood flow)			X		X		X	X	
Physical Characteristics (assessed pre-dose) ¹²	X	X	X	X	X		X	X	
Clinical Characteristics ¹³	X		X	X	X	X	X	X	
Concomitant Medication Review			X	<=====>				X	X
Adverse Event Assessment ¹⁴			X	<=====>				X	X

1. Optional Baseline Run In visit: This optional visit is for subjects that will exceed the 14 (± 1 day) Run-in window between screening and Day 1.
2. Single ECGs will be taken at Screening and pre-dose on Day 1 and 24h post-last dose on Day15. ECGs should be taken while subject is supine for at least 5 minutes. Additional ECGs may be taken at the discretion of the investigator as needed based on symptoms or ECG findings.

3. Assessment of vital signs (including blood pressure and heart rate) will be performed at Screening and pre-dose on Days 1, 7, 15 (24h post-last dose), and at Follow-up Visits. Vital signs should be performed after resting in a supine or semi-supine position for at least 5 minutes.
4. Blood samples for safety will be collected fasting at Screening and pre-dose/equivalent time on Days 1, 7, 15 (24h post-last-dose), and at the 7-10 day Follow-up Visit. Refer to Section 7.2.4 for specific laboratory parameters to be tested.
5. See Item 7 in the Inclusion Criteria – DFU Subjects for acceptable perfusion parameters. Only 1 test of the 4 (TcPO₂, ABI, toe pressure, Doppler ultrasound) is required for eligibility.

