4.6.3. Serial PK Time and Events Table Part B

VIST DAY	Part B Serial PK Sampling ^{1,2}								
	Pre-dose	Hours (h)							
		1h	2h	4h	8h	10h	11h	12h	24h
Day 1	X		X						
Day 7	X		X						
Day 14 OUT-PATIENTS	X	X	X	X	X	X ³			X
Day 14 IN-PATIENTS	X	X	X	X	X			X	X

1. Patients are permitted to either stay in clinic (in-patients) or be discharged and return for clinic visits (out-patients). Refer to Section 7.12 for details on the collection and processing of PK samples.
2. PK sampling times may be changed based on observed GSK1278863 PK profile.
3. Sample must be taken within the 10 to 12 hour time window.

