Based on data from Part A it was decided that there would only be one cohort in part B.

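### The overnight-stay instruction in Protocol 4.2.2.3 does not except the Day 14 stay; followed there, it produces an unscheduled 15th application on Day 15

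*Protocol*

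**What the plan says.** Section 4.2.2 of the Protocol sets the length of Part B dosing: "For each cohort, subjects will undergo repeat applications of GSK1278863 or placebo, at the dose chosen for that cohort for 14 days". Section 4.2.2.3 lists the days. "Applications of study drug will be done in clinic on Days 1, 4, 7, and 14", and the subject applies the ointment on Days 2–3, 5–6 and 8–13. Section 1.4.1.3 also places the last dose on Day 14.

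The next paragraph of Section 4.2.2.3 deals with days of serial PK sampling. Subjects may leave after the 8 h sample if they can return within the 10 to 12 h window. For those who do not leave, it says: "If subjects elect to stay overnight, they should be encouraged to apply the study ointment and complete the diary entries themselves" before they are discharged in the morning. It adds that staff can use the occasion for further instruction. It names no day and excepts none.

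Footnote 1 to the serial PK table in Section 4.6.3 makes the stay optional: "Patients are permitted to either stay in clinic (in-patients) or be discharged and return for clinic visits (out-patients"). The table gives Days 1 and 7 a pre-dose and a 2 h sample only. Day 14 runs to 24 h and has separate rows, one for out-patients and one headed "Day 14 IN-PATIENTS".

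In the Part B Time and Events Table (Section 4.6.2), the clinic dosing row has no mark on Day 15. Footnote 2 times the final ECG at "24h post-last dose on Day15", and footnotes 3 and 4 time vital signs and safety labs in the same way. Section 4.2.2.4 counts follow-up from the end of dosing: "Follow-up visits will occur 7 to 10 days and 28 to 32 days following completion of dosing".

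**The concern.** The dosing list and the overnight instruction agree for stays after Day 1 and Day 7. They disagree for the stay after Day 14, which is the one the current PK table specifically provides for. The sampling pattern described in the overnight paragraph (8 h, then 10 to 12 h) now exists only on Day 14.

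Three things follow if the sentence is applied to that stay:

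- **An extra application unrelated to the assigned regimen.** In-patients would receive a dose that out-patients do not, because they chose to stay.
- **Day 15 data.** The 24 h PK sample, ECG, vital signs, safety labs, biopsy, wound fluid, SensiLase and wound measurement all fall on Day 15. They are timed either from the last dose or at a time equivalent to pre-dose. If ointment goes on before them, those time labels are wrong. If it goes on afterwards, the Day 15 data are unaffected.
- **The follow-up anchor.** In either order the last dose moves to Day 15, and both follow-up windows move with it. The SAP's Exhibit A compares follow-up with Day 1, by group and between groups.

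**Working it through.** **Inputs**

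- Clinic application days: 1, 4, 7, 14 (Protocol 4.2.2.3).
- Self-application days: 2–3, 5–6, 8–13 (Protocol 4.2.2.3).
- Serial PK days: 1, 7, 14 (Protocol 4.6.2, footnote 9, and 4.6.3).
- Follow-up: 7 to 10 and 28 to 32 days after dosing ends (Protocol 4.2.2.4).
- Repeat-dose regimen: 1% ointment at 100 mg/cm² (SAP Section 7).
- Ulcer area at randomisation: 1 to 16 cm² (Protocol 5.3.1, criterion 6c).
- Part B cohort: 12 active, 2 placebo, 2 standard of care (SAP 3.1). One cohort only: "it was decided that there would only be one cohort in part B" (SAP Section 3).

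**1. The plan's own count**

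Clinic: 4. Self-applied: 2 + 2 + 6 = 10. Total: 4 + 10 = 14, covering Days 1 to 14 once each with no overlap. This reproduces the 14 days of dosing in Section 4.2.2.

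**2. The overnight instruction applied to each serial PK day**

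| Stay after | Next morning | Application scheduled? | Total applications |
|---|---|---|---|
| Day 1 | Day 2 | Yes | 14 |
| Day 7 | Day 8 | Yes | 14 |
| Day 14 | Day 15 | No | 15 |

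The excess is 1/14 = 7.1%.

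**3. Follow-up windows**

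| Last dose | First window | Second window |
|---|---|---|
| Day 14 | 14 + 7 to 14 + 10 = Days 21–24 | 14 + 28 to 14 + 32 = Days 42–46 |
| Day 15 | 15 + 7 to 15 + 10 = Days 22–25 | 15 + 28 to 15 + 32 = Days 43–47 |

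A visit booked for Day 21 would be 21 − 15 = 6 days after the last dose, below the minimum of 7. One booked for Day 42 would be 42 − 15 = 27 days after it, below the minimum of 28. Visits on Days 22–24 and 43–46 are valid either way.

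**4. Size of the extra active dose**

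100 mg/cm² × 1% = 1 mg of drug per cm². For 1 cm² this is 1 mg; for 16 cm² it is 16 mg.

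**5. How many subjects**

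Standard-of-care subjects apply no study ointment, so the ceiling is 12 + 2 = 14 of the 16 planned. The share who stay after Day 14 is not given, so the range is 0 to 14, before any replacements.

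**The case against.** The strongest reply is that no Day 15 dose is intended and the documents show it repeatedly. The sentence sits under a heading for 14-day dosing, directly after a complete list of days that ends at Day 14. Section 1.4.1.3 names Day 14 as the last dose, the Time and Events Table has no Day 15 dosing mark, and its footnotes label Day 15 as 24 h after the last dose. Section 4.1 makes adherence to that table mandatory, whereas the overnight sentence only encourages. Read with the remark about further instruction, the sentence can be taken to say who should apply a dose that is due, as practice for home use. After Day 14 no home dosing remains to practise. The dosing card and the Study Procedures Manual, which are not available here, may also state the stop day.

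The reply continues that the consequences are small. Harm needs a subject who stays on Day 14, staff who follow the sentence against the schedule, and ointment actually applied. The old and new follow-up windows largely overlap. The Amendment 7 rationale reports systemic concentrations below the assay limit (0.10 ng/mL) in patients given 1% at 100 mg/cm². An overnight stay is not tied to arm, so no bias between arms is shown. No formal hypotheses are tested, and the wound endpoints are exploratory.

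Most of this stands as a limit on impact. It establishes the intention and makes it likely that a careful site avoids the error. It does not remove the problem. The instruction is explicit and excepts no day. On the stay that the current PK table mainly provides for, following it means departing from the mandatory table. That the intention is clear elsewhere is a reason to make this sentence agree with it.

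**Conclusion.** The concern holds. Within the current text of Section 4.2.2.3, the overnight instruction is correct for stays after Days 1 and 7 and wrong for the stay after Day 14. The effect is low and conditional: it arises only if a subject stays after Day 14 and the sentence is followed. Day 15 measurements are compromised only if the ointment is applied before they are taken. Outside-window follow-up arises only for visits kept on the first permitted day of the original window.

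The drug amount assumes the SAP's repeat regimen and an ulcer within the randomisation limits at the time of application. It is applied mass, not systemic exposure, and the documents give no basis for calling it a major safety risk. The number affected cannot be narrowed below the ceiling of 14 without the share of overnight stays.

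**What to change.** Add to Section 4.2.2.3 that overnight self-application applies only when the next morning is a scheduled self-application day, that is, Day 2 after a Day 1 stay or Day 8 after a Day 7 stay. State that no ointment is applied after the Day 14 dose. Put the same statement in the site instruction.

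The cost is one clause and the matching site wording. No visit, sample or procedure is added, and no analysis changes.

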4.2.2.4. Follow-up Visits

Follow-up visits will occur 7 to 10 days and 28 to 32 days following completion of dosing. Any subject withdrawing from the trial prematurely will also be asked to complete all follow-up procedures.

See Section [4.6](#) for details regarding all study procedures performed during the course of this trial.

4.3. Treatment Assignment

This will be a single-blind study. Treatments will be blinded to subjects and the investigator site staff only. GSK study staff is not blinded.

Subjects will be assigned to receive GSK1278863A or vehicle (placebo) in Part A and GSK1278863A or vehicle or SOC only (moist occlusion) in Part B in accordance with the randomization schedule generated by GSK Discovery Biometrics, prior to the start of the study, using validated internal software.

Subjects will be randomized into the study by means of an interactive voice response system (IVRS) to receive one of the treatment regimens listed in the below tables ([Table 2](#) and [Table 3](#)).

Table 2 Part A Doses

Cohort	Regimen	Dose (mg)	Treatment Area by Period	
			1	2
1	P	Placebo ¹	Intact	Intact
	A	0.3mg		
	B	TBD ²		
2	P	Placebo	Intact	Wound
	C	TBD		
3	P	Placebo	Wound	N/A
	D	TBD		
4(or final)	P	Placebo	Wound	Intact
	E	TBD		
O (Optional) ³	P	Placebo	Wound	N/A
	F	TBD		

1. Placebo = vehicle
 2. Actual doses to be determined as preliminary PK data are reviewed and predicted exposures can be calculated.
 3. More than one optional cohort may be used.

Table 3 Part B Doses

Cohort ¹	Regimen	Dose (mg)
5	P	Placebo ²
	S	Standard of Care
	F ³	TBD
6	P	Placebo
	S	Standard of Care
	G	TBD
7	P	Placebo
	S	Standard of Care
	H	TBD

1. Cohort numbering may be different based on the number of cohorts conducted in Part A
2. Placebo = vehicle
3. Starting dose may be adjusted based upon evaluation of PK data from Part A

In Part A

For Cohorts 2 through 4, drug volume to be administered will be based on wound area. See Section 11 for details.

An example of planned doses of GSK1278863 and regimen designation for Part A is in [Table 4](#).

Table 4 Example Treatment Options

Cohort	Regimen/ Dosing Period	Dose (mg)	Treatment Area
1 (HVT)	P1	Placebo ¹	Intact Skin
	A	0.3 mg	Intact Skin
	P1	Placebo	Intact Skin
	B	TBD ²	Intact Skin
2	P1	Placebo	Intact Skin
	C1	TBD	Intact Skin
	P2	Placebo	Wound
	C2	TBD	Wound
3	P2	Placebo	Wound
	D	TBD	Wound
4(or final)	P2	Placebo	Wound
	E1	TBD	Wound
	P1	Placebo	Intact Skin
	E2	TBD	Intact Skin
O (Optional) ³	P2	Placebo	Wound
	F	TBD	Wound

1. Placebo = vehicle

2. Actual doses to be determined as preliminary PK data are reviewed and predicted exposures can be calculated.

3. More than one optional cohort may be used.

In Part B

Drug volume to be administered will be based on wound area, which may vary during the treatment period. See Section 4.4 for details. Actual doses will be chosen based on preliminary PK data (data permitting, See Section 4.2.1.6) from Part A.

